	Drug type and cumulative sedative dose	**	**	**	**	**	***	***
	APACHE IV STOP-BANG SOFA			**	*		***	***
	Age, sex, race/ethnicity		*		**	**		
Patient-reported Health Status	PROMIS Global Health					*	***	***
Patient-reported Sleep Quality	PROMIS-SD PROMIS-SRI					*	***	***
Patient-reported Cognitive Function	PROMIS-CF PROMIS-CFA					*	***	***
Cognitive Function	NIH Toolbox Cognition Battery					*	*	*

Note:

* = Data collection in person (measures shaded in grey are temporarily paused)

** = Data collection from the electronic medical record

*** = Data collection via telephone or video conference visit (measures highlighted in yellow are telephone- or video-collected substitutes for in-person visits)

We plan to review approximately 350 medical records in order to achieve our sample size of 182 enrollments during the 4-year study. The data collection schedule is shown in Table 2.

IRB Study Number: 20170771, Version #1.8, Date: 03/10/21, PI: [name]

Table 2. Study Timeline

Activity	Year	Year 1			Year 2			Year 3			Year 4		
	Months	1-4	5-8	9-12	1-4	5-8	9-12	1-4	5-8	9-12	1-4	5-8	9-12
Hire/train personnel													
Database refinement													
Subject recruitment and enrollment													
Subject 1 and 6 month follow up													
Data collection													
Data management													
Analysis of final results													
Final results manuscript													
Final grant report													

8. Study Endpoints

Primary Endpoint. To test the effect of the Family Automated Voice Reorientation (FAVoR) intervention on delirium in critically ill, mechanically ventilated adults during hospitalization in the ICU, we plan for 95% power respectively to detect an effect size (W) of 0.35 using a 2 degrees of freedom Chi-Square Test with a significance level (alpha) of 0.05.

Secondary Endpoint. The recently completed BRAIN-ICU descriptive study of ICU survivors reported a 43% attrition from the inpatient sample to a 12 month follow up time point.¹⁸ Given that a secondary aim of the proposed project plans 1month and 6 months post-hospital discharge follow up, we conservatively planned for a 40% attrition rate, which is a sample size of 182 total (91 in each group).

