The timeframe chosen for intervention delivery coincides with usual waking hours; no message will be played outside of this timeframe so as not to disturb sleep or interrupt family visits in the evening hours. Further, early morning hours are typically times of patient care intensity and additional stimulation at that time may not be appropriate. Based on our preliminary studies we found that by placing the speaker near the patient's ear, the recorded message is able to be heard at a volume that is loud enough for the patient but not so loud as to be noxious or interfere with care providing activities; the message will be loud enough for the patient to hear comfortably but not loud enough to be excessively stimulating or irritating to the normal listener. Although the use of earphones to deliver the message might focus the subject's attention on the message, we chose not to use earphones as these would also block out other stimuli and potentially result in greater disorientation. In addition, earphones could impair understanding of communication to the subjects from providers or family.

IRB Study Number: 20170771, Version #1.8, Date: 03/10/21, PI: [name]

Sources of Materials

Data will be obtained both inpatient and outpatient from the patient's medical record, noninvasive physiologic monitoring, cognitive testing (delirium assessment and NIH Toolbox Cognition Battery), and observation. Data will include patient's gender, age, race, ethnic background, reason for admission to the ICU, pharmacological therapies affecting cognition and sleep, laboratory data to calculate the APACHE III, SBM and SOFA, wrist actigraphy, sleep profiler-polysomnography, cognitive testing (delirium and NIH Toolbox Cognition Battery) scores and PROMIS global health scores. Only study personnel who are responsible for enrolment and data collection will have access to individually identifiable information. Each subject will be assigned an arbitrary study identification number, and no individually identifiable private information will be entered into the study database.

Key Variables and Their Measurement

Please refer to Table 1 for a detailed list of which data can only be collected in person. To protect human subjects, we are closely following the COVID-19 safety recommendations.

Therefore, we will pause data collection for the following 4 measures at JMH until enrollment resumes, and during followup visits:

1. CAM-ICU (substituted by CAM)
2. Actigraphy

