3. SP-PSG (substituted by PROMIS-SD and PROMIS-SRI)
4. NIH Toolbox Cognition Battery (substituted by PROMIS-CF and PROMIS-CFA)

Delirium. The primary outcome measure for this project is delirium free days. We will quantify delirium using the Confusion Assessment Method for the ICU (CAM-ICU).⁴⁵ CAM-ICU scores for each subject will be obtained by study personnel twice daily at 9 am and 4 pm (coinciding with the schedule for initiation and conclusion of messages each day in the FAVoR intervention group, and at identical times for the control group). CAM-ICU scores will also be recorded at the same times for two days following the completion of the intervention period. The Confusion Assessment Method (CAM) will be used during study visits after transfer from the ICU (post ICU, 1 month, and 6 month follow up periods) for comparison.

We will also collect documentation by providers in the medical record of episodes of delirium occurring outside of the CAM-ICU data collection conducted by research personnel. Only days without any instances of delirium will be counted as delirium free days. The CAM-ICU is recognized in the Clinical Practice Guidelines for the Management of Pain, Agitation, and Delirium in Adult Patients in the Intensive Care Unit as a valid, reliable, and feasible tool to detect delirium in ICU patients³ with pooled sensitivity of 75.5% and specificity of 95.8%.⁵⁰

Sleep/Activity. Sleep patterns in the critically ill are highly disorganized, with fragmentation, a predominance of light sleep, and reduction in deep sleep and rapid eye movements.⁸ We will use the FDA approved Sleep Profiler system (Advanced Brain Monitoring, Carlsbad, CA) to obtain continuous polysomnography data (SPPSG). The Sleep Profiler has been successfully utilized in mechanically ventilated and sedated patients and provides three frontopolar electroencephalographic (EEG) signals (AF7/AF8, AF7/Fpz and AF8/Fpz).⁵¹⁻⁵⁴

A wrist actigraph (ActiWatch Spectrum, Philips Respironics, Bend, OR) will be placed on the wrist to measure patient activity and ambient light levels. We have extensive experience with

IRB Study Number: 20170771, Version #1.8, Date: 03/10/21, PI: [name]

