There will be two parts of the data analysis: Part I: A traditional statistical data analysis for randomized controlled trials for the Primary Specific Aim, and Part II: Pathway analytic model analyses to address the secondary aims. [name] will work closely with the Data Manager to perform all the planned data analyses for this study.

Part I: We will follow the research and regulatory guidelines for statistical analysis of clinical trials including the ICH Guideline⁷⁷ and the CONSORT guidelines⁷⁸. First, descriptive statistics will be performed to describe and compare the characteristics of the intervention and the control groups. Descriptive statistics will be reported as means +/- standard deviation for continuous variables and as frequencies and percentages for categorical variables. Shapes of the data distributions, missing data and outliers will be examined by both graphics and statistical tests. Any data issues identified will be discussed with the PI and other investigators and addressed before formal data analysis. For example, skewed variables may be transformed so that their distributions are close to the Normal Distribution. Outliers may be excluded or included in two separate analyses. Missing data may be imputed or handled by other missing data techniques. Distributions of continuous variables and categorical variables will be compared between the intervention and the control group by using the t-test or Wilcoxon rank sum test and the Chisquare test, respectively. Any baseline covariate that is differentially distributed in the two groups will be adjusted in the subsequent analysis for testing the intervention effect. Assuming the randomization produces well balanced intervention and control groups, a Chi-square test for a 2x2 table with the number of delirium free days and the treatment assignment will be performed to test the primary hypothesis. If there are unbalanced covariates, then covariance adjustment will be performed by using logistic regression that includes both the treatment assignment and the unbalanced covariates. If there are missing values in the primary outcome, then multiple imputation will be performed using SAS PROC MI for missing at random (MAR) data.^{79,80} Sensitivity analysis for potentially not missing at random data will be performed using the Yau and Little⁸¹ Intent-to-Treat Analysis for Longitudinal Studies with Dropouts.

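### The primary model is chosen by testing the randomised arms for baseline imbalance, with no threshold or covariate list, so it is not fixed in advance

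*Combined protocol and SAP*

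**What the plan says.** Section 10, Data Analysis Plan, Part I, compares baseline distributions between the arms by t-test or Wilcoxon test for continuous variables and by chi-square for categorical ones. It then gives the selection rule: "Any baseline covariate that is differentially distributed in the two groups will be adjusted in the subsequent analysis for testing the intervention effect".

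Two primary tests follow from it. The first depends on the outcome of that comparison: "Assuming the randomization produces well balanced intervention and control groups, a Chi-square test for a 2x2 table", applied to delirium-free days and treatment assignment. The second replaces it when balance fails: "If there are unbalanced covariates, then covariance adjustment will be performed by using logistic regression", with treatment and the unbalanced covariates in the model.

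No p-value or standardised difference says when a covariate counts as unbalanced, and no covariates are named for adjustment. Nothing elsewhere fills the gap. Section 9 (Sample) describes permuted-block randomisation and names no stratification factor that could serve as a fixed covariate. Section 9 (Disease Severity and Comorbid Conditions) calls the evidence for APACHE severity as a delirium risk factor strong, but does not make it a covariate.

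**The concern.** Under valid randomisation, any baseline difference between the arms is chance. A covariate therefore enters the primary model because of luck in allocation, not because it predicts delirium. Three things follow.

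- Which of two primary tests is run, and with which covariates, is unknown until the arms have been compared.
- With no threshold stated, whoever does the comparison has room for judgement.
- A factor that the plan itself regards as prognostic is usually omitted, so the plan takes on the complexity of adjustment and gets little of its benefit.

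At stake are mainly the prespecification of the primary analysis and, to a smaller extent, its power.

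**Working it through.** **The plan's own figure.** Section 8 says "we plan for 95% power respectively to detect an effect size (W) of 0.35" with alpha 0.05 and 2 df, and gives N = 182 (91 per arm). Power comes from a noncentral chi-square with noncentrality N x W². At N = 182 this is 182 x 0.1225 = 22.3, giving power 0.992 on 2 df and 0.997 on the 1 df of a 2x2 table. The 95% target is reached at 127 (2 df) or 107 (1 df). The point below does not rest on this figure, but it shows that there is almost no power left to gain at W = 0.35.

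**Chance that the primary test switches.** For k independent candidates tested at level a, the chance that at least one is flagged is 1 - (1 - a)^k. Both k and a are assumptions, because the plan gives neither.

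- a = 0.05: k = 5 gives 1 - 0.95^5 = 0.226; k = 10 gives 0.401; k = 15 gives 1 - 0.95^15 = 0.537.
- a = 0.10: 0.410, 0.651 and 0.794 for the same k.

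Correlation between candidates lowers these figures. For example, with 12 candidates at 0.05 the chance is 0.460 if they are independent and 0.360 at a common correlation of 0.4. Any single covariate, APACHE included, is flagged with probability a, so at 0.05 it is left out about 95% of the time.

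**Power, by simulation** (20,000 trials, 91 per arm, Wald tests in logistic models, selection threshold 0.05). All of the following are assumptions: a binary any-delirium outcome; control risk 65%; 12 candidates, of which APACHE, age and a three-level study-admission CAM-ICU carry prognostic information in varying strength. The effects are risk reductions of 21 and 17 points. A 21-point reduction takes risk from 65% to 44%, so W = 0.21 / (2 x √(0.545 x 0.455)) = 0.21 and the odds ratio is (0.44/0.56) / (0.65/0.35) = 0.42.

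| Log-odds per SD, APACHE / age | Effect (points) | Unadjusted | Plan's rule | APACHE + age always |
|---|---|---|---|---|
| 0.2 / 0.2 | 21 | 81.4% | 81.2% | 82.7% |
| 0.5 / 0.3 (CAM-ICU uninformative) | 21 | 81.2% | 81.5% | 84.8% |
| 0.5 / 0.3 (CAM-ICU moderate) | 21 | 81.0% | 81.3% | 84.3% |
| 0.7 / 0.5 | 21 | 80.8% | 81.3% | 85.9% |
| 0.2 / 0.2 | 17 | 63.3% | 63.0% | 64.9% |
| 0.5 / 0.3 (CAM-ICU uninformative) | 17 | 64.2% | 64.1% | 68.0% |
| 0.5 / 0.3 (CAM-ICU moderate) | 17 | 62.6% | 62.5% | 66.1% |
| 0.7 / 0.5 | 17 | 63.0% | 63.8% | 69.3% |

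The fixed model gains between 82.7 - 81.2 = 1.5 and 69.3 - 63.8 = 5.5 points over the rule. The noncentral chi-square gives 80.9% (W = 0.21) and 63.1% (W = 0.17), in line with the unadjusted column. At the planned W = 0.35 (control risk 67.5%), unadjusted power is 99.8%, and the rule and the fixed model each give 99.8% to 99.9%.

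A smaller simulation (4,000 trials, 12 covariates, two of them prognostic at log-odds 0.5 and 0.3, effect of roughly 21 points) gives 81.2%, 81.2% and 84.2%.

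**Other operating characteristics.**

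- Type I error of the rule with the threshold fixed at 0.05: 4.6% to 5.0%. In another simulation with 10 covariates, three of them prognostic, and thresholds of 0.05 or 0.20: 3.2% to 4.5%.
- The two branches disagree on p < 0.05 in 2.2% to 3.6% of trials at the 21-point effect.
- The odds ratio at that effect is 0.42 unadjusted and 0.38 to 0.42 given APACHE and age.

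**The case against.** Adjusting for observed imbalance is familiar practice. Part I also places the baseline comparison first and the test of the intervention afterwards. That order stands, and nothing in the text describes choosing covariates after seeing outcomes. A reader might infer that the rule inflates type I error. With one threshold fixed in advance it does not. Error reaches 5.6% to 6.4% only if the analyst could pick between no adjustment, 0.05 and 0.10 once outcomes are known, and the plan says nothing of the kind.

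It can be said that candidates are in fact listed, for instance "Data will include patient's gender, age, race, ethnic background, reason for admission to the ICU". That is a list of data to be collected; no item in it is designated for adjustment. The alpha of 0.05 in Section 8 belongs to the power of the primary test, not to the baseline comparisons. The promise in Part I to resolve data issues before formal analysis concerns distributions, missing data and outliers, and supplies no balance criterion. If balance were judged by eye rather than by test, the model would be less fixed still.

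A reader might also infer that most covariates entering by chance would be irrelevant to delirium. The documents point the other way. Section 9 says that demographic characteristics and sensory deficits may bear on delirium, and Section 4 lists drug therapies and comorbid conditions among theorised factors, while calling the evidence limited. The fault is that entry does not depend on prognostic value, not that the variables have none.

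The strongest part of the objection is size. At the planned effect the choice hardly matters, and every power gain shown rests on effect sizes, control risk and prognostic strengths that the documents do not give. That stands.

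**Conclusion.** The point holds as one of prespecification, and the plan should be changed. The primary model is not determined in advance, and no other section determines it. That conclusion needs no numerical assumption.

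The size of the consequence does rest on assumptions, and it is modest. The switching range depends on the assumed number of candidates, their independence and the threshold. The gain of roughly 2 to 6 points from always adjusting for APACHE and age depends on a 17- to 21-point effect, the assumed prognostic strengths and a binary outcome, which Part I does not define. The assumed CAM-ICU mix (35% negative, 25% positive, 40% unable to assess) sits poorly with the 89% sedated or delirious cited in Section 5. Changing it to 11/19/70% moves APACHE-plus-age power only from 85.9% to 85.6% in the strongest scenario.

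A reader might infer a serious loss of power. One simulation with three independent predictors at log-odds 1.0 per SD does show 66% for a fixed model against 50% for the rule, but nothing in the documents supports three predictors of that strength.

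**What to change.** Delete the imbalance rule and the two conditional branches from Part I. Before outcomes are seen by arm, state the following:

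- The primary model always contains treatment, ICU-admission APACHE and age, whatever the observed balance.
- One APACHE version is used throughout. Sources of Materials in Section 9 has "laboratory data to calculate the APACHE III, SBM and SOFA", while Disease Severity in Section 9 and Table 1 name APACHE IV; these must be reconciled first.
- Missing covariate values are handled in the same multiple-imputation model as the outcome. At present the general provision is only "Missing data may be imputed or handled by other missing data techniques".
- The unadjusted test is reported as supportive.
- The baseline table is descriptive, without significance tests.

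Always using the unadjusted chi-square would also fix the model, but would give up the small gain at lesser effects. The binary form of the outcome must be defined before either test can be run; that is a separate matter.

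The cost is SAP wording only. Age and APACHE are already collected, so there are no new data and no change to N.

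### The primary test needs a two-level outcome, but the primary outcome is a count of delirium free days with no stated cut, and the sample size is set for a different test

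*Combined protocol and SAP*

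**What the plan says.** - Outcome (Section 9, Key Variables, Delirium): "The primary outcome measure for this project is delirium free days". A single day is defined: "Only days without any instances of delirium will be counted as delirium free days". No rule sorts patients into two groups by their number of such days.
- Test (Section 10, Data Analysis Plan, Part I): "a Chi-square test for a 2x2 table with the number of delirium free days and the treatment assignment will be performed". If baseline covariates are unbalanced, "covariance adjustment will be performed by using logistic regression that includes both the treatment assignment and the unbalanced covariates".
- Sample size (Section 8, Primary Endpoint): 95% power "to detect an effect size (W) of 0.35 using a 2 degrees of freedom Chi-Square Test" at alpha 0.05. The total is 182, 91 per group, after 40% attrition that Section 8 ties to post-discharge follow-up.
- A different primary outcome (Section 4, design summary before Preliminary Studies): the number of delirium episodes over the ICU stay.
- Time frames: the aim concerns delirium while in the ICU (Sections 3 and 10). Both arms are in the study period for five days or until earlier ICU discharge (Section 9, Group Assignment). In addition, "CAM-ICU scores will also be recorded at the same times for two days following the completion of the intervention period".
- Missing data (Section 10, Part I): "If there are missing values in the primary outcome, then multiple imputation will be performed using SAS PROC MI", under missing at random. Also, "Sensitivity analysis for potentially not missing at random data will be performed".

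**The concern.** A count cannot enter a 2x2 table or a binary logistic regression until someone chooses a cut. Because the protocol does not choose one, the primary p-value depends on a decision that could still be taken once outcomes by arm are visible. The stated power does not settle the matter, because it belongs to a test with a different number of outcome levels. At stake are the 5% error rate, if the cut is chosen with knowledge of the data, and the power, which depends strongly on where the cut falls.

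**Working it through.** **1. Outcome levels implied by each section.** A table with r outcome levels and two arms has (r − 1)(2 − 1) degrees of freedom.
- Section 10, 2x2 table: r = 2, so 1 df.
- Section 8, 2 df: r − 1 = 2, so r = 3.
- Section 9, count of delirium free days: 0 to 5 is six levels. If the two extra CAM-ICU days count, 0 to 7 is eight.

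One outcome therefore has two, three, or six to eight levels, depending on the section.

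**2. The plan's own sample size.** Power is the probability that a noncentral chi-square with noncentrality N × w² exceeds the 5% critical value. With w = 0.35, w² = 0.1225.
- 2 df: 95% power needs N = 127. Then 127 × 1.4 = 178 and 127 / 0.6 = 212. Starting from 130, 130 × 1.4 = 182 exactly (power at 130 is 95.6%).
- 1 df: 95% power needs N = 107. Then 107 / 0.6 = 179.

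So 182 is approached from 2 df by multiplying by 1.4, or from 1 df by dividing by 0.6. The total does not reveal which test was meant.

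Power at w = 0.35:

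| Test | N = 182 | N = 109 (182 × 0.6) |
|---|---|---|
| 1 df | 99.7% | 95.5% |
| 2 df | 99.2% | 91.6% |

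The right-hand column applies only if the follow-up attrition is also taken to affect the ICU outcome. For a two-level outcome, w = |p1 − p2| / (2√(p̄(1 − p̄))). With 80% vs 46.2%, p̄ = 0.631 and w = 0.338 / (2 × 0.4825) = 0.35. The protocol states no such pair of proportions.

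**3. How much the cut matters (illustrative).** Inputs from the protocol: 91 per arm (Section 8); delirium onset 2.6 days (SD 1.7) and duration 3.4 days (SD 1.9) (Section 9, Intervention Group); up to 80% delirious when ventilated (Section 4). Assumptions: gamma shapes, a 7-day window opening one day after ICU admission, every day observed, and the effects in the table. The cut is at least k delirium free days, so k = 7 is no delirium versus any. Entries are the percentage of simulated trials that reject at 0.05.

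| Scenario | k=1 | 2 | 3 | 4 | 5 | 6 | 7 | Rank-sum |
|---|---|---|---|---|---|---|---|---|
| Mixed: 80 to 65%, duration 3.4 to 2.6 days | 21 | 48 | 67 | 75 | 70 | 62 | 60 | 86 |
| Incidence only: 80 to 60% | 6 | 9 | 17 | 33 | 54 | 79 | 84 | 66 |
| Duration only: 3.4 to 2.2 days | 32 | 71 | 86 | 86 | 54 | 9 | 5 | 72 |
| Planned w = 0.35: 80 to 46% | 9 | 21 | 42 | 74 | 95 | 99 | 100 | 99 |

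With no effect, each fixed cut rejects in 4–5% of trials and the rank-sum test in 4.8%. Reporting whichever cut gives the smallest p-value rejects in 20.9% (16.5% with a 5-day window). Reruns with other seeds moved these figures by up to about three points.

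**4. Window and unobserved days.** Three time frames stand side by side: the ICU stay, five days or ICU discharge, and two CAM-ICU days after the intervention period. None is tied to the analysed count. Section 12 stops research data collection at study completion or withdrawal, and Section 13 (Protections Against Risk) limits in-hospital data to the point of a repeated vital-sign fluctuation. Neither section, nor Section 10, says whether the days after these points, or after ICU discharge, are missing, delirium free, or outside the count. Imputation cannot be specified until that is settled.

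**The case against.** The strongest reply is that the intended table is obvious: any delirium versus none, one row per patient. Section 4 describes prevention and lower occurrence, which fits that reading. At the planned effect it has about 100% power, so the extreme low cuts in the table are ones nobody would choose. That is fair. It weakens the wide power range as a forecast, but not the defect: Section 10 refers to the number of days, Section 8 to a 2 df test, and Section 4 to episodes. Even under this reading, the window and the unobserved days stay open.

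It can also be said that the aim supplies a window (the ICU stay), that imputation and a not-missing-at-random analysis are planned, and that data kept only up to a cut-off suggest later days are missing. These points stand in part. The aim gives a time frame but does not choose between the five-day and the extended CAM-ICU schedules, and the imputation plan does not say which days it covers.

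A reader might go further and infer that the table pools patient-days as independent units. The documents do not support this. Subjects are randomised, the sample size is in subjects, and the pilot p-value in Section 4 does not show which unit was used. A reader might also infer that a rank test is required. It is not: it does better when incidence and duration both fall, and worse than any-versus-none when only incidence falls, which is the effect Section 4 emphasises.

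**Conclusion.** The point holds, and it should be fixed before outcomes are compared by arm. The contradiction between Sections 4, 8, 9 and 10 is on the page and needs no simulation: the test as written cannot be applied to the outcome as written, and the powered test is not the planned one.

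The magnitudes are illustrative. The figure of about 20% is a worst case that requires choosing the cut after seeing the data; nothing in the protocol shows that this was done or intended. The 21% to 76% range belongs to the assumed mixed effect, with assumed shapes and a fully observed 7-day window. No figure is given for the effect of early discharge or death, because the documents give no rates to base one on. Low power overall should not be inferred either: at w = 0.35 with 182 patients, both the 1 df and the 2 df test exceed 99%.

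**What to change.** Before any outcome is examined by arm, amend Sections 4, 8, 9 and 10 so that they agree on:

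1. **One primary outcome**, one row per patient, over one stated window.
2. **One analysis that fits it.** Either keep the 2x2 chi-square and logistic regression with a single stated cut (any delirium versus none fits the prevention aim), or analyse the count with a rank-sum test. The choice is the sponsor's. The trade-off is about 86% for the rank test against at most about 76% for any cut in the mixed case, and about 66–69% against 84% for any-versus-none if only incidence falls. A proportional-odds model for covariate adjustment would need its assumption checked.
3. **Unobserved days.** State which days after ICU discharge, study completion or data cut-off are missing and enter the planned multiple imputation, and add one sensitivity analysis under the alternative handling.
4. **Power.** Restate Section 8 for the chosen test. For a chi-square at w = 0.35 the figures are in the working. Say whether the 40% attrition applies to the ICU outcome.

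The cost is an amendment and a new power statement. Some chart review may be needed if days after ICU discharge are to be scored, since Table 1 schedules only one inpatient research CAM at that stage (24–72 hours after ICU discharge), alongside provider documentation.
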